11 DATA HANDLING AND RECORD KEEPING

Data collection is the responsibility of the clinical trial staff under the supervision of the PI. The investigator is ultimately responsible for ensuring the accuracy, completeness, legibility, and timeliness of the data reported.

All source documents should be completed in a neat, legible manner to ensure accurate interpretation of data. When making changes or corrections, cross out the original entry with a single line, and initial and date the change. Do not erase, overwrite, or use correction fluid or tape on the original source data.

Case Report Forms (CRFs) will be utilized to capture data in the clinical study. Data collection processes and procedures will be reviewed and validated to ensure completeness, accuracy, reliability and consistency.

The PI and study team will conduct periodic reviews of the source data records and CRF database for completeness, consistency and accuracy. Study data will be collected and reported to the DSMB as required by the data and safety monitoring plan.

11.1 Records Retention

FDA investigational drug and device regulations, and GCP guidelines state that clinical trial records and essential documents should be retained for a minimum of 2 years after the last approval of a marketing application, or if no application is to be filed or if the application is not approved, at least 2 years have elapsed since the formal discontinuation or conclusion of the clinical trial. Refer to SOP #CTO-04 for maintenance and archiving of clinical trial records.

11.2 Disclosure and Publication Policy

This study will comply with the FDAAA regulations and NIH policy for registration and results reporting in the ClinicalTrials.gov database, as applicable. The International Committee of Medical Journal Editors (ICMJE) member journals have adopted a clinical trials registration policy as a condition for publication. Registration of the study in the ClinicalTrials.gov database prior to study initiation will comply with this policy.

The principal investigator will be responsible for developing publication procedures and resolving authorship issues.

12 ETHICAL AND REGULATORY CONSIDERATIONS

12.1 Institutional Review

The Institutional Review Board will review the application, protocol and all appropriate documentation in order to safeguard the rights, safety, and well-being of study subjects. The study will only be conducted at study centers where IRB approval has been obtained. The final study protocol, including the final version of the Informed Consent Form, must be approved or given a favorable opinion in writing by the IRB. If the protocol is amended, changes will not be implemented without prior review and approval from the IRB, except where necessary to eliminate an immediate hazard to study subjects.

12.2 Data and Safety Monitoring Plan

A review will take place of any adverse events that have occurred after every sixth subject has completed the study. Meetings/conference calls with members of the research team will be used as needed to discuss problems and make recommendations as an ongoing process throughout the study.

The clinical trial may be selected for audit within the scope of the Internal Audit Program. The purpose of an audit is to determine and evaluate adherence to applicable federal regulations, to the study protocol and to GCP principles. The PI is responsible for working with the auditor in providing all needed study records and for developing corrective actions where necessary and ensuring complete and adequate responses to internal audit findings.

If the study is selected for an FDA or other federal agency inspection, the PI will make requested study records and study personnel records available for review (refer to SOP REG-01: FDA Inspections).

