| MedDRA | Medical Dictionary for Regulatory Activities |
| MTD | Maximum Tolerated Dose |
| NIH | National Institutes of Health |
| NIDDK | National Institute of Diabetes and Digestive and Kidney Diseases |
| PI | Principal Investigator |
| rtCGM | Real-time continuous glucose monitoring |
| SAE | Serious Adverse Event |

STATEMENT OF COMPLIANCE

I confirm that I have read this protocol, and I will conduct the study as outlined herein and according to the ethical principles stated in the latest version of the Declaration of Helsinki, the U.S. code of federal regulations (CFR) applicable to clinical studies (45 CFR Part 46, 21 CFR Part 50, 21 CFR Part 56, 21 CFR Part 312 and/or 21 CFR Part 812), and the applicable ICH guidelines for Good Clinical Practice (GCP).

I will promptly submit the protocol to the IRB for review and approval. Once the protocol has been approved by the IRB, I understand that any modifications made during the course of the study must first be approved by the IRB prior to implementation except when such modification is made to remove an immediate hazard to the subject.

I will provide copies of the protocol and all pertinent information to all individuals responsible to me who assist in the conduct of this study. I will discuss this material with them to ensure that they are fully informed regarding the study treatment, the conduct of the study, and the obligations of confidentiality.

Note: This document is signed electronically through submission and approval by the Principal Investigator in the University of Utah IRB Electronic Research Integrity and Compliance Administration (ERICA) system.

STUDY SUMMARY

| Title | The Use of Amitriptyline for Improving Hypoglycemia Recognition and Course | | | |
|---------------------------|--|--|--|--|
| Short Title | Amitriptyline as an anti-hypoglycemic agent | | | |
| Protocol Number | IRB # 00110853 | | | |
| IND | Pending – applying for IND exemption | | | |
| Phase | Pilot, clinical phase II | | | |
| Design | Double blind, randomized, placebo control, cross- over design | | | |
| Study Duration | 38 weeks | | | |
| Study Center(s) | University of Utah Hospital and Clinics | | | |
| Objectives | To evaluate whether amitriptyline improves the hypoglycemia course and the ability to recognize hypoglycemia in type 1 diabetes patients who are using real-time continuous glucose monitoring devices | | | |

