4.2 Number of Subjects

Up to 80 participants are expected to be enrolled into the study for the Run-in Period assessment. For the study drug testing phase, 24 participants will be randomized and equally divided into two arms (i.e., 12 participants in the amitriptyline arm and 12 participants in the matching placebo arm).

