4.4 Study Duration

The pilot study is expected to last for two years, and will help provide the estimated time for the final study. The duration of each patient's participation in the study will be 39 weeks, with 15 weeks of active assessment/intervention and 24 weeks of distant follow-up.

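### The only scheduled adverse-event review waits for six study completers, on the plain reading to Week 39, by when 13 to 24 of the 24 subjects are randomised, depending on accrual

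*Combined protocol and SAP*

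**What the plan says.** Section 12.2 fixes the timing of the review: "A review will take place of any adverse events that have occurred after every sixth subject has completed the study". The same section adds team meetings or calls as needed throughout the study. It names no reviewing body and does not say what counts as completion.

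Section 4.4 states that each patient's "participation in the study will be 39 weeks", made up of "15 weeks of active assessment/intervention and 24 weeks of distant follow-up". The Study Summary gives 38 weeks instead. Under Section 4.2, "24 participants will be randomized and equally divided into two arms", after as many as 80 have entered the run-in.

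The Study Calendar (Section 8) puts randomisation at Week 3 and marks adverse-event assessment at Weeks 3, 5, 7, 11 and 13. It marks none at the Week 27 and 39 telephone calls. Section 9.11.1, however, has collection continue to the last follow-up visit.

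Section 11 assumes a board: "Study data will be collected and reported to the DSMB as required by the data and safety monitoring plan".

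**The concern.** A periodic review is there to see patterns that single-event handling misses, such as an accumulation of non-serious events, early enough to matter for people not yet dosed. Here it is tied to the end of a long follow-up with no dosing and no marked adverse-event assessment. On the plain reading, most of the trial is randomised before the first look.

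The trigger also responds the wrong way to toxicity. Section 7 withdraws subjects who have serious or intolerable drug-related events, and Section 6.3 lets withdrawn subjects be replaced. If such subjects do not count as completers, more withdrawals mean a later review.

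**Working it through.** **Inputs from the documents.** 24 randomised (4.2); participation 15 + 24 = 39 weeks (4.4), which reproduces the plan's own figure; randomisation at Week 3 and last marked adverse-event assessment at Week 13 (8); about 12 weeks of treatment (6.3); two years in total, taken as 104 weeks (4.4).

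**Assumption.** No accrual rate or recruitment window is given. The base case is even randomisation over T = 104 − 39 = 65 weeks, so that the last subject finishes within two years. T is varied from 48 to 104 weeks.

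**Lags.**
- Week 39 trigger: L = 39 − 3 = 36 weeks after randomisation (37 if counted to the end of Week 39).
- Visit 4 trigger: L = 13 − 3 = 10 weeks.
- End of active phase (Week 15): L = 15 − 3 = 12 weeks.
- Wait beyond the last marked assessment: 39 − 13 = 26 weeks.

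**Formula.** First review = randomisation time of subject 6, plus L. Number randomised by then ≈ 6 + 24 × L / T, then counted exactly with randomisations spaced T/23 or T/24 weeks apart.

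**Base case, Week 39 trigger.** The approximation is 6 + 24 × 36 / 65 = 19.3. Exact count at spacing 65/23 = 2.83 weeks: subject 6 is randomised at 5 × 2.83 = 14.1, so the review falls at 14.1 + 36 = 50.1 weeks. By then 18 are randomised (50.1 / 2.83 = 17.7, so 17 after the first). Those past 12 weeks of dosing number 14 ((50.1 − 12) / 2.83 = 13.5, so 13 after the first). The other spacing gives 19 randomised.

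**Randomised at the first review, of 24:**

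| Window T (weeks) | Week 39 trigger | Visit 4 trigger |
|---|---|---|
| 48 | 23–24 | 10–11 |
| 52 | 21–23 | 10 |
| 65 | 18–19 | 9 |
| 78 | 16–17 | 8–9 |
| 90 | 15 | 8 |
| 104 | 13–14 | 8 |

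At T = 39 or less, all 24 are randomised under the Week 39 trigger. Using the Study Summary's 38 weeks at T = 65 gives 18. With random instead of even arrivals at T = 65, the mean is 19.3 and the 5th to 95th percentile is 15 to 23.

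**Alternative meaning of completion.** If it is the end of the active phase, 10 of 24 are randomised at T = 65.

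**Second review, Week 39 trigger.** All 24 are randomised at T = 65, but only 19 to 20 at T = 104. With the Visit 4 trigger at T = 65, the second review falls at about week 41 with 15 randomised.

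**Effect of withdrawals.** If two of the first eight are withdrawn and do not count, the eighth randomised subject becomes the sixth completer. At T = 65 the review moves from about week 50 to about week 56, with 20 to 21 randomised instead of 18 to 19 (replacements ignored).

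**The case against.** The strongest reply is that the scheduled review is a secondary layer. This is a 24-subject, single-centre pilot of an approved drug at what the protocol calls a low dose. Adverse events are assessed at five points up to Week 13. Related serious events and intolerable toxicities end treatment (7), the investigator may withdraw a subject (6.3), reports to the FDA are due in 7 or 15 calendar days and to the IRB in 10 working days (9.11.3), the study stops if risk to benefit is worse than expected (9.12), and the team meets as needed. All of this stands and limits the harm. What it does not supply is a fixed point at which accumulated events are examined together.

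Three stronger readings are tempting and are not supported:
- **That three quarters of the trial is randomised before the first review.** No accrual figure is given; 18 to 19 of 24 depends on the 65-week assumption. Nor is completion settled as Week 39: Section 4.4 separates an active phase from distant follow-up, and the end-of-active-phase reading largely removes the problem.
- **That the review cannot protect anyone.** In the base case 5 to 6 are not yet randomised at the first review and 4 to 5 more are still within 12 weeks of dosing. At T = 104, 10 to 11 are not yet randomised.
- **That withdrawn subjects' events escape review, or that follow-up yields nothing.** Section 12.2 covers any adverse events that have occurred, so withdrawn subjects' events are in scope; only their effect on the count is in doubt. Section 9.11.1 collects events to the last follow-up visit and asks at phone contacts, and Section 9.10.2 counts severe hypoglycaemia at calls. The calendar disagrees on adverse events, and the two need reconciling.

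**Conclusion.** The point holds in a conditional form. On the plain reading, the one scheduled review waits about 26 weeks beyond the last marked adverse-event assessment and can inform the care of few later participants. The size rests on two assumptions: that completion means Week 39, and that accrual is even. With accrual over about 65 weeks, 18 to 19 of 24 are randomised at the first review; for 104 to 48 weeks the range is 13 to 24. The direction does not depend on the window: under the Week 39 reading more than half are randomised for any window up to 104 weeks, against 8 to 11 with a Visit 4 trigger for windows of 104 to 48 weeks.

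The mismatch between the board in Section 11 and the silence of Section 12.2 is a separate documentation fault. It does not bear on the timing.

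**What to change.** In Section 12.2, keep the count of six and change the trigger to: *has reached Visit 4 (Week 13) or stopped study drug, whichever is first*. This settles the undefined term and lets subjects who stop for toxicity advance the count. State also how replacements are counted and that run-in failures are not. In the base case the first review then falls about 24 to 26 weeks after the first randomisation, with 9 of 24 randomised.

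Cost: one sentence, and some information arrives later. Visit 4 precedes the taper, so the triggering subject's taper and the Week 27 and 39 calls are seen only at the next review; this matters because Section 3 lists drug-withdrawal effects. At T = 65, five of the first six are already past 12 weeks of dosing at the first review, so little taper information is deferred. Counting both stoppers and their replacements may add a review.

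Also reconcile three pairs of statements: the calendar and Section 9.11.1 on adverse-event collection after Week 13; Sections 11 and 12.2 on who receives the review; and the 38 and 39 weeks given for duration.

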12.3 Protocol Deviations

A protocol deviation (or violation) is any departure from the defined procedures and treatment plans as outlined in the protocol version submitted and previously approved by the IRB. Protocol deviations have the potential to place participants at risk and can also undermine the scientific integrity of the study thus jeopardizing the justification for the research. Protocol deviations are unplanned and unintentional events.

Because some protocol deviations pose no plausible threat to participant safety or scientific integrity, reporting is left to the discretion of the PI within the context of the guidelines below. The IRB requires the **prompt reporting** (within 10 working days) of protocol deviations which are:

- Exceptions to eligibility criteria
- Intended to eliminate apparent immediate hazard to a research participant
- Harmful caused harm to participants or others, or placed them at increased risk of harm, including physical, psychological, economic, or social harm
- Possible serious or continued noncompliance

12.4 FDA Annual Reporting

If this study requires IND approval, within 60 days of the anniversary date that the IND went into effect, a brief report of the progress of the investigation will be submitted to the FDA following the requirements set out in 21 CFR Part 312.33.

12.5 Clinical Trials Database

The clinical trial will be registered at initiation and study results will be reported on the ClinicalTrials.gov database as required per 42 CFR Part 11.

